7.2.2.4. Summaries of Laboratory Abnormalities

Laboratory data that are categorical will be summarized using the number and percentage of participants in the study with the given response at baseline and each scheduled postbaseline visit.

The following summaries (number and percentage of participants) will be provided by lab test and cohort; within cohort 2, the summary will be presented by treatment group (Group A or Group B). Participants will be categorized according to the most severe postbaseline abnormality grade for a given lab test:

- Graded laboratory abnormalities
- Grade 3 or 4 laboratory abnormalities

For all summaries of laboratory abnormalities, the denominator is the number of participants with nonmissing postbaseline values.

The above summaries will be provided for 1) TE laboratory abnormalities, 2) non-TE laboratory abnormalities, and 3) laboratory abnormalities through FU W24.

By-participant listings of all laboratory abnormalities, and Grade 3 or 4 laboratory abnormalities will be provided by cohort, participant ID number and visit in chronological order. The listings will include all test results that were collected throughout the study for the lab test of interest, with all applicable severity grades or abnormal flags displayed.

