3.1.5. Follow-Up (FU) Analysis Set

The FU Analysis Set includes all participants who have at least 1 follow-up visit, after completing or premature discontinued from the study drugs.

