7.2.1. Summaries of Numeric Laboratory Results

Descriptive statistics (n, mean, SD, median, Q1, Q3, minimum, and maximum) will be provided for each cohort (and for each treatment group for Cohort 2) for chemistry (including alanine aminotransferase [ALT], aspartate aminotransferase [AST], total bilirubin, alkaline phosphatase [ALP], creatine kinase [CK], fasting total cholesterol, fasting glucose, international normalized ratio [INR], lactate dehydrogenase [LDH]), creatinine, and eGFR_{CG} as follows:

- Baseline values
- Values at each postbaseline visit
- Change from baseline at each postbaseline visit

A baseline laboratory value will be defined as the last measurement obtained on or prior to the date of first dose of any study drug. Change from baseline to a postbaseline visit will be defined as the visit value minus the baseline value. The mean, median, Q1, Q3, minimum, and maximum values will be displayed to the reported number of digits; SD values will be displayed to the reported number of digits plus 1.

Median (Q1, Q3) of the observed values for ALT will be plotted using a line plot by treatment group and visit.

In the case of multiple values in an analysis window, data will be selected for analysis as described in Section 3.8.3.

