7.2.2.2. Non-TE Laboratory Abnormalities

Non-TE laboratory abnormalities are defined as values that increase at least 1 toxicity grade from the last TE laboratory abnormality after the composite last on-treatment date plus 30 days. If the relevant TE laboratory abnormality for a participant is missing, any abnormality of at least Grade 1 observed after the composite last on-treatment date plus 30 days until the end of the study will be consider as non-TE.

7.2.2.3. Laboratory Abnormalities Through FU Week 24

Laboratory abnormalities through FU Week 24 are defined as values that increase at least 1 toxicity grade from baseline at any postbaseline time point, up to and including the composite last on-treatment date plus 24 weeks. If the relevant baseline laboratory value is missing, any abnormality of at least Grade 1 observed within the time frame specified above will be considered as within FU Week 24.

Definitions of the composite last on-treatment date for each cohort can be found in Section 3.8.2.

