7.2.3. Liver-related Laboratory Evaluations

The following liver-related laboratory abnormalities will be summarized using the number and percentage of participants for any postbaseline measurements as follows:

- Confirmed ALT flare: ALT > $2 \times \text{baseline}$ and $\geq 5 \times \text{ULN}$
- Confirmed ALT elevation: $\geq 10 \times \text{ULN}$

- Confirmed ALT elevation with evidence of hepatic toxicity: ALT > 2 × nadir and one of the following confirmed laboratory abnormalities:
 - Total bilirubin $> 2 \times ULN$
 - Elevated INR > 0.5 above baseline and > ULN
 - Abnormal serum ALB > 1 g/dL decrease from baseline

Central Lab ULNs will be used for all liver-related laboratory evaluations.

For individual laboratory tests, participants will be counted once based on the most severe postbaseline values during the analysis period. For the composite criteria of ALT and total bilirubin, INR or ALB, participants will be counted once when the criteria are met at the same postbaseline visit date. The denominator is the number of participants in the Safety Analysis Set who have nonmissing postbaseline values of all relevant tests at the same postbaseline visit date.

ALT flare and confirmed ALT elevations will be summarized by cohort; within Cohort 2, the summary will be presented by treatment group (Group A or Group B).

The above summaries will be provided for 1) TE laboratory abnormalities, 2) non-TE laboratory abnormalities; 3) laboratory abnormalities through FU Week 24.

Listings of participants who met at least 1 of the above criteria for ALT flares and elevations will be provided. For the listings of ALT flares and elevations, AST (U/L), ALB (g/dL), total bilirubin (mg/dL), INR, HBsAg (log₁₀ IU/mL) and HBV DNA (log₁₀ IU/mL) will also be provided.

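### The non-treatment-emergent laboratory tables have no period-specific denominator, so, read literally, participants with no sample after the cut-off count as event-free

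*SAP*

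**What the plan says.** SAP Section 7.2.2.4 gives a single rule for the graded laboratory tables: "For all summaries of laboratory abnormalities, the denominator is the number of participants with nonmissing postbaseline values". The next sentence lists the tables it governs: "The above summaries will be provided for 1) TE laboratory abnormalities, 2) non-TE laboratory abnormalities, and 3) laboratory abnormalities through FU W24".

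Section 7.2.2.2 defines a non-TE abnormality by "values that increase at least 1 toxicity grade from the last TE laboratory abnormality after the composite last on-treatment date plus 30 days". If there is no earlier treatment-emergent abnormality to compare with, any abnormality of Grade 1 or above in that same later period counts. Either way, only values after the cut-off can make a case.

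Section 7.2.1 settles where postbaseline begins: "A baseline laboratory value will be defined as the last measurement obtained on or prior to the date of first dose of any study drug". On-treatment values are therefore postbaseline values.

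Section 7.2.3 (ALT flare, ALT elevation, ALT elevation with hepatic toxicity) has its own rule: "The denominator is the number of participants in the Safety Analysis Set who have nonmissing postbaseline values of all relevant tests", taken at one visit date. These tables are also produced for the treatment-emergent, non-TE and through-FU-Week-24 periods.

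Section 3.1.5 defines a set for participants with follow-up: "The FU Analysis Set includes all participants who have at least 1 follow-up visit". The SAP uses it only in the disposition counts of Section 4.1.

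**The concern.** The denominator rule in Section 7.2.2.4 leaves out participants who could not have been observed to have an abnormality. That works for the treatment-emergent and through-FU-Week-24 tables, whose periods start at first dose. It fails for the non-TE table, where the observation period moves to after the cut-off and the denominator does not move with it. A participant sampled on treatment but never after the cut-off cannot enter the numerator, yet stays in the denominator as a non-case.

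The non-TE liver tables are where hepatic flares after the end of treatment will be read. The error runs one way: it can only lower the reported rate.

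**Working it through.** The SAP states no figure on this point, so there is nothing to reproduce. The check compares the two observation periods and then works out the dilution.

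**Step 1: who can be a non-TE case.** Section 3.8.2 counts FU Day from the composite last on-treatment date, so the cut-off is FU Day 30 and non-TE values start at FU Day 31.

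**Step 2: which scheduled samples fall after the cut-off** (Table 3-10 and the schedules in SAP Appendix 1).
- FU Week 4: nominal FU Day 29, visit window ±5 days, so FU Days 24 to 34. An on-time sample is before the cut-off; one on FU Days 31 to 34 is after it.
- FU Week 8: a telephone visit with no safety laboratory tests in the current schedule. Table 3-10 still keeps an analysis window for it (FU Days 44 to 71), so any value recorded then would count.
- FU Week 12: nominal FU Day 85, the first scheduled laboratory visit that lies wholly after the cut-off.
- Early discontinuation visit: safety laboratory tests are scheduled in both cohorts, within 14 days of notification.

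The affected participants are therefore those with on-treatment samples and nothing after FU Day 30. An example is someone lost at or before FU Week 4 with no later early-discontinuation or unscheduled sample.

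**Step 3: the dilution.** Let n be participants with a postbaseline value, m the share of them with no value after the cut-off, and p the rate among those sampled.
- Expected cases = p × n(1 - m)
- As written: p × n(1 - m) / n = p(1 - m)
- Denominator restricted to sampled participants: p × n(1 - m) / [n(1 - m)] = p

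The SAP gives neither m nor p. Assumed values:

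| m | as written, p = 20% | as written, p = 10% |
|---|---|---|
| 0% | 20% | 10% |
| 5% | 19% | 9.5% |
| 10% | 18% | 9% |
| 20% | 16% | 8% |
| 30% | 14% | 7% |

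In counts, take Cohort 1 or Cohort 2 Group A at the planned n = 40, with m = 20% and p = 20%. Sampled: 40 × 0.80 = 32. Expected cases: 32 × 0.20 = 6.4. As written: 6.4/40 = 16%. Among those sampled: 6.4/32 = 20%. For Group B at n = 20: 16 sampled, 3.2 expected cases, 3.2/20 = 16% against 3.2/16 = 20%.

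**Step 4: would the FU Analysis Set solve it?** No. A follow-up visit without blood sampling, such as the FU Week 1 telephone visit in Cohort 2, is enough to enter that set. The denominator has to be specific to test and period.

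**The case against.** The best defence is that the wording is ambiguous, not wrong. Section 7.2.2.4 uses the same unqualified word, postbaseline, for the worst grade in the numerator, and nobody would let on-treatment grades into the non-TE table. Section 7.2.3 ties its worst values to the analysis period. A programmer might read the denominator the same way. That is possible, but neither section says so, and a rule stated for all summaries points the other way. The ambiguity is itself a reason to write the restriction down.

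It is also fair that the tables are descriptive, no test is affected, and the listings show every abnormality and every participant meeting the flare or elevation criteria. No event is hidden; only the percentages are affected.

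A further objection is that the restricted rate is a complete-case rate, valid for the whole cohort only if unsampled participants resemble sampled ones. This stands. But the literal rule assumes that no unsampled participant had an event, which is the lowest possible value. At m = 20% and p = 20%, the cohort rate could lie anywhere from 0.20 × 0.80 = 16% to 16% + 20% = 36%. Printing the N makes the gap visible under either choice.

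Four stronger readings are tempting and are not supported:
- That everyone leaving before FU Week 12 lacks a non-TE value. Early-discontinuation samples, late FU Week 4 samples and any value in the retained FU Week 8 window can all fall after the cut-off.
- That Section 7.2.3 repeats the rule of Section 7.2.2.4. Its rule is different and follows directly on the composite criteria. It shares only the missing period. If it covers only the composites, the single-test ALT criteria still have no period-specific denominator.
- That non-TE adverse event tables have the same fault. Section 7.1.7.2 states no denominator, and adverse events are also collected at telephone visits.
- That the rule distorts the comparison of Groups A and B. It would if m differed between them, but the SAP gives no dropout by group.

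**Conclusion.** The point holds on the text. The non-TE laboratory summaries in Sections 7.2.2.4 and 7.2.3 have no denominator matched to the period in which a non-TE abnormality can be seen. Followed literally, the reported rate is the rate among sampled participants times (1 - m).

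The size depends wholly on m, which the document does not give. The loss is nil with complete follow-up. Under an assumed rate of 20% it is 1 percentage point at m = 5% and 6 points at m = 30%. Because several routes can give early leavers a sample after the cut-off, m covers only those with none of them. This is a safety-reporting correction worth making; it does not touch the efficacy analyses or any error rate.

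**What to change.** In Section 7.2.2.4, add that for the non-TE tables the denominator is participants with at least one nonmissing value of that test later than 30 days after the composite last on-treatment date. In Section 7.2.3, add the same restriction for the non-TE tables. For the composite criteria, require all relevant tests at one visit date after that cut-off. Say explicitly which denominator the single-test ALT criteria use. Print the resulting N in each non-TE table.

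The treatment-emergent and through-FU-Week-24 denominators can stay as they are.

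The cost is a sentence or two in each of two sections and one programming filter. Section 1 already provides for changes after SAP finalization to be documented in the CSR. The downside is slightly smaller denominators, which may differ from test to test, and less favourable percentages.

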7.2.3. Liver-related Laboratory Evaluations

The following liver-related laboratory abnormalities will be summarized using the number and percentage of participants for any postbaseline measurements as follows:

- Confirmed ALT flare: ALT > $2 \times \text{baseline}$ and $\geq 5 \times \text{ULN}$
- Confirmed ALT elevation: $\geq 10 \times \text{ULN}$

- Confirmed ALT elevation with evidence of hepatic toxicity: ALT > 2 × nadir and one of the following confirmed laboratory abnormalities:
 - Total bilirubin $> 2 \times ULN$
 - Elevated INR > 0.5 above baseline and > ULN
 - Abnormal serum ALB > 1 g/dL decrease from baseline

Central Lab ULNs will be used for all liver-related laboratory evaluations.

For individual laboratory tests, participants will be counted once based on the most severe postbaseline values during the analysis period. For the composite criteria of ALT and total bilirubin, INR or ALB, participants will be counted once when the criteria are met at the same postbaseline visit date. The denominator is the number of participants in the Safety Analysis Set who have nonmissing postbaseline values of all relevant tests at the same postbaseline visit date.

ALT flare and confirmed ALT elevations will be summarized by cohort; within Cohort 2, the summary will be presented by treatment group (Group A or Group B).

The above summaries will be provided for 1) TE laboratory abnormalities, 2) non-TE laboratory abnormalities; 3) laboratory abnormalities through FU Week 24.

Listings of participants who met at least 1 of the above criteria for ALT flares and elevations will be provided. For the listings of ALT flares and elevations, AST (U/L), ALB (g/dL), total bilirubin (mg/dL), INR, HBsAg (log₁₀ IU/mL) and HBV DNA (log₁₀ IU/mL) will also be provided.

7.3. Body Weight, Height, and Vital Signs

Descriptive statistics will be provided by cohort (and by treatment group for Cohort 2) for body weight, height, BMI, and vital signs as follows:

- Baseline value
- Values at each postbaseline visit
- Change from baseline at each postbaseline visit

A baseline value will be defined as the last available value collected on or prior to the date/time of first dose of study drug. Change from baseline to a postbaseline visit will be defined as the postbaseline value minus the baseline value. Body weight and vital signs measured at unscheduled visits will be included for the baseline value selection.

In the case of multiple values in an analysis window, data will be selected for analysis as described in Section 3.8.3. No formal statistical testing is planned.

A by-participant listing of vital signs will be provided by participant ID number and visit in chronological order. Body weight, height, and BMI will be included in the vital signs listing if space permits. If not, they will be provided separately.

7.4. Prior HBV and Concomitant Medications

Medications collected at screening and during the study will be coded using the current version of the World Health Organization (WHO) Drug dictionary.

7.4.1. Prior HBV Medications

Prior HBV medications are defined as any medications taken before a participant took any of the study drugs.

Prior HBV medications will be summarized by preferred name using the number and percentage of participants by cohort (and by treatment group for Cohort 2). A participant reporting the same medication more than once will be counted only once when calculating the number and percentage of participants who received that medication. The summary will be ordered by preferred term in order of descending overall frequency. For drugs with the same frequency, sorting will be done alphabetically.

For the purposes of analysis, any medication with a start date prior to the first dosing date of study drug will be included in the prior medication summary regardless of when the stop date is. If a partial start date is entered the medication will be considered prior unless the month and year (if day is missing) or year (if day and month are missing) of the start date are after the first dosing date. Medications with a completely missing start date will be included in the prior medication summary, unless otherwise specified.

Summaries will be based on the Safety Analysis Set. No formal statistical testing is planned.

7.4.2. Concomitant Medications

Concomitant medications are defined as medications taken while a participant took study drug. Use of concomitant medications will be summarized by preferred name using the number and percentage of participants for each treatment group. A participant reporting the same medication more than once will be counted only once when calculating the number and percentage of participants who received that medication. The summary will be ordered by preferred term in descending overall frequency. For drugs with the same frequency, sorting will be done alphabetically.

For the purposes of analysis, any medications with a start date prior to or on the first dosing date of study drug and continued to be taken after the first dosing date or started after the first dosing date but prior to or on the last dosing date of study drug will be considered concomitant medications. Medications started and stopped on the same day as the first dosing date, or the last dosing date of study drug will also be considered concomitant. Medications with a stop date prior to the date of first dosing date of study drug or a start date after the last dosing date of study drug will be excluded from the concomitant medication summary. If a partial stop date is entered, any

medication with the month and year (if day is missing) or year (if day and month are missing) prior to the date of first study drug administration will be excluded from the concomitant medication summary. If a partial start date is entered, any medication with the month and year (if day is missing) or year (if day and month are missing) after the study drug stop date will be excluded from the concomitant medication summary. Medications with completely missing start and stop dates will be included in the concomitant medication summary, unless otherwise specified. Summaries will be based on the Safety Analysis Set. No formal statistical testing is planned.

All prior and concomitant medications (other than per-protocol study drugs) will be provided in a by-participant listing sorted by participant ID number and administration date in chronological order.

7.5. Electrocardiogram Results

Electrocardiogram (ECG) analysis results are intended to identify meaningful abnormalities. If potential abnormalities of interest are identified, further analyses may be conducted.

A shift table of the investigators' assessment of ECG results at Weeks 12 and 36 for Cohort 1 and Cohort 2 Group A, or Weeks 12 and 24 for Cohort 2 Group B compared with baseline values will be presented by cohort (and by treatment group for Cohort 2) using the following categories: normal; abnormal, not clinically significant; abnormal, clinically significant; or missing. The number and percentage of participants in each cross-classification group of the shift table will be presented. Participants with a missing value at baseline or postbaseline will not be included in the denominator for percentage calculation. No formal statistical testing is planned.

A by-participant listing for ECG assessment results will be provided by participant ID number and visit in chronological order.

7.6. Other Safety Measures

For Cohort 1 and Cohort 2 Group A, ophthalmic examinations will be performed at Screening, Week 24, and Week 36. For Cohort 2 Group B, ophthalmic examinations will be performed at Screening, Week 12, and Week 24.

A shift table of the overall assessment of ophthalmology results at each visit compared with baseline values will be presented for each cohort (and for each treatment group for Cohort 2) using the following categories: normal; abnormal, not clinically significant; abnormal, clinically significant; or missing/unknown. The number and percentage of participants in each cross-classification group of the shift table will be presented. Participants with a missing value at baseline or postbaseline will not be included in the denominator for percentage calculation. No formal statistical testing is planned.

By-participant listings for ophthalmology assessment results will be provided by participant ID number and visit in chronological order.

8. PHARMACOKINETIC (PK) ANALYSES

Only SLGN PK Analysis will be performed for this study.

8.1. PK Sample Collection

For Cohort 1 and Cohort 2 Group A, sparse (timed) blood PK samples will be obtained at Baseline/Day1 (predose and postdose), Weeks 12 and 20 at any time between 1 to 5 hours postdose relative to SLGN administration unless otherwise indicated.

For Cohort 2 Group B, sparse (timed) blood PK samples will be obtained at Baseline/Day1, Weeks 12 and 20 at any time between 1 to 5 hours postdose relative to SLGN administration unless otherwise indicated.

8.2. PK Analyses Related to Intensive PK Sampling

8.2.1. Estimation of PK Parameters

PK parameters will be estimated using Phoenix WinNonlin® software using standard noncompartmental method. The linear up/log down rule will be used in conjunction with the appropriate noncompartmental model, with input values for dose level, dosing time, plasma concentration, and corresponding real-time values, based on drug dosing times whenever possible.

All predose sample times before time-zero will be converted to 0.

For area under the curve (AUC), samples BLQ of the bioanalytical assays occurring prior to the achievement of the first quantifiable concentration will be assigned a concentration value of 0 to prevent overestimation of the initial AUC. Samples that are BLQ at all other time points will be treated as missing data in WinNonlin. The nominal time point for a key event or dosing interval (τ) may be used to permit direct calculation of AUC over specific time intervals. The appropriateness of this approach will be assessed by the PK scientist on a profile-by-profile basis.

Pharmacokinetic parameters such as AUC_{tau} , λ_z and $t_{1/2}$ are dependent on an accurate estimation of the terminal elimination phase of drug. The appropriateness of calculating these parameters will be evaluated upon inspection of PK data on a profile-by-profile basis by the PK scientist.

